III. Volitional movement mixing synergies, without compensation				
Hand to lumbar spine hand on lap	cannot perform or hand in front of ant-sup iliac spine hand behind ant-sup iliac spine (without compensation) hand to lumbar spine (without compensation)			
Shoulder flexion 0° - 90° elbow at 0° pronation-supination 0°	immediate abduction or elbow flexion abduction or elbow flexion during movement flexion 90°, no shoulder abduction or elbow flexion			
Pronation-supination elbow at 90° shoulder at 0°	no pronation/supination, starting position impossible limited pronation/supination, maintains starting position full pronation/supination, maintains starting position			
Subtotal III (max 6)				
IV. Volitional movement with little or no synergy				
Shoulder abduction 0° - 90° elbow at 0° forearm neutral	immediate supination or elbow flexion supination or elbow flexion during movement abduction 90°, maintains extension and pronation			
Shoulder flexion 90° - 180° elbow at 0° pronation-supination 0°	immediate abduction or elbow flexion abduction or elbow flexion during movement flexion 180°, no shoulder abduction or elbow flexion			
Pronation/supination elbow at 0° shoulder at 30°- 90° flexion	no pronation/supination, starting position impossible limited pronation/supination, maintains start position full pronation/supination, maintains starting position			
Subtotal IV (max 6)				
V. Normal reflex activity assessed only if full score of 6 points is achieved in part IV; compare with the unaffected side				
Biceps, triceps, finger flexors	2 of 3 reflexes markedly hyperactive 1 reflex markedly hyperactive or at least 2 reflexes lively maximum of 1 reflex lively, none hyperactive			
Subtotal V (max 2)				
Total A (max 36)				

B. WRIST support may be provided at the elbow to take or hold the starting position, no support at wrist, check the passive range of motion prior testing		none	partial	full
Stability at 15° dorsiflexion elbow at 90°, forearm pronated shoulder at 0°	less than 15° active dorsiflexion dorsiflexion 15°, no resistance tolerated maintains dorsiflexion against resistance	0	1	2
Repeated dorsiflexion / volar flexion elbow at 90°, forearm pronated shoulder at 0°, slight finger flexion	cannot perform volitionally limited active range of motion full active range of motion, smoothly	0	1	2
Stability at 15° dorsiflexion elbow at 0°, forearm pronated slight shoulder flexion/abduction	less than 15° active dorsiflexion dorsiflexion 15°, no resistance tolerated maintains dorsiflexion against resistance	0	1	2
Repeated dorsiflexion / volar flexion elbow at 0°, forearm pronated slight shoulder flexion/abduction	cannot perform volitionally limited active range of motion full active range of motion, smoothly	0	1	2
Circumduction elbow at 90°, forearm pronated shoulder at 0°	cannot perform volitionally jerky movement or incomplete complete and smooth circumduction	0	1	2
Total B (max 10)				

C. HAND support may be provided at the elbow to keep 90° flexion, no support at the wrist, compare with unaffected hand, the objects are interposed, active grasp		none	partial	full
Mass flexion from full active or passive extension		0	1	2
Mass extension from full active or passive flexion		0	1	2
GRASP				
a. Hook grasp flexion in PIP and DIP (digits II-V), extension in MCP II-V	cannot be performed can hold position but weak maintains position against resistance	0	1	2
b. Thumb abduction 1-st CMC, MCP, IP at 0°, scrap of paper between thumb and 2-nd MCP joint	cannot be performed can hold paper but not against tug can hold paper against a tug	0	1	2
c. Pincer grasp, opposition pulpa of the thumb against the pulpa of 2-nd finger, pencil, tug upward	cannot be performed can hold pencil but not against tug can hold pencil against a tug	0	1	2
d. Cylinder grasp cylinder shaped object (small can) tug upward, opposition of thumb and fingers	cannot be performed can hold cylinder but not against tug can hold cylinder against a tug	0	1	2
e. Spherical grasp fingers in abduction/flexion, thumb opposed, tennis ball, tug away	cannot be performed can hold ball but not against tug can hold ball against a tug	0	1	2
Total C (max 14)				

D. COORDINATION/SPEED , sitting, after one trial with both arms, eyes closed, tip of the index finger from knee to nose, 5 times as fast as possible		marked	slight	none
Tremor		0	1	2
Dysmetria	pronounced or unsystematic slight and systematic no dysmetria	0	1	2
		≥ 6s	2 - 5s	< 2s
Time start and end with the hand on the knee	6 or more seconds slower than unaffected side 2-5 seconds slower than unaffected side less than 2 seconds difference	0	1	2
Total D (max 6)				

1-2 TIS

Item

Static sitting balance	
1	Starting position Patient falls or cannot maintain starting position for 10 seconds without arm support  0
	Patient can maintain starting position for 10 seconds  2
	If score = 0, then TIS total score = 0
2	Starting position Therapist crosses the unaffected leg over the hemiplegic leg Patient falls or cannot maintain sitting position for 10 seconds without arm support  0
	Patient can maintain sitting position for 10 seconds  2
3	Starting position Patient crosses the unaffected leg over the hemiplegic leg Patient falls  0 Patient cannot cross the legs without arm support on bed or table  1 Patient crosses the legs but displaces the trunk more than 10 cm backwards or assists crossing with the hand  2 Patient crosses the legs without trunk displacement or assistance  3 Total static sitting balance  7
Dynamic sitting balance	
1	Starting position Patient is instructed to touch the bed or table with the hemiplegic elbow (by shortening the hemiplegic side and lengthening the unaffected side) and return to the starting position Patient falls, needs support from an upper extremity or the elbow  0 does not touch the bed or table  1 Patient moves actively without help, elbow touches bed or table  1 If score = 0, then items 2 and 3 score 0
2	Repeat item 1 Patient demonstrates no or opposite shortening/lengthening  0 Patient demonstrates appropriate shortening/lengthening  1 If score = 0, then item 3 scores 0
3	Repeat item 1 Patient compensates. Possible compensations are: (1) use of upper extremity, (2) contralateral hip abduction, (3) hip flexion (if elbow touches bed or table further than proximal half of femur), (4) knee flexion, (5) sliding of the feet Patient moves without compensation  1
4	Starting position Patient is instructed to touch the bed or table with the unaffected elbow (by shortening the unaffected side and lengthening the hemiplegic side) and return to the starting position Patient falls, needs support from an upper extremity or the elbow  0 does not touch the bed or table  1 Patient moves actively without help, elbow touches bed or table  1 If score = 0, then items 5 and 6 score 0
5	Repeat item 4 Patient demonstrates no or opposite shortening/lengthening  0 Patient demonstrates appropriate shortening/lengthening  1 If score = 0, then item 6 scores 0

Item

6	Repeat item 4	Patient compensates. Possible compensations are: (1) use of upper extremity, (2) contralateral hip abduction, (3) hip flexion (if elbow touches bed or table further than proximal half of femur), (4) knee flexion, (5) sliding of the feet Patient moves without compensation	 0  1
7	Starting position Patient is instructed to lift pelvis from bed or table at the hemiplegic side (by shortening the hemiplegic side and lengthening the unaffected side) and return to the starting position	Patient demonstrates no or opposite shortening/lengthening Patient demonstrates appropriate shortening/lengthening If score = 0, then item 8 scores 0	 0  1
8	Repeat item 7	Patient compensates. Possible compensations are: (1) use of upper extremity, (2) pushing off with the ipsilateral foot (heel loses contact with the floor) Patient moves without compensation	 0  1
9	Starting position Patient is instructed to lift pelvis from bed or table at the unaffected side (by shortening the unaffected side and lengthening the hemiplegic side) and return to the starting position	Patient demonstrates no or opposite shortening/lengthening Patient demonstrates appropriate shortening/lengthening If score = 0, then item 10 scores 0	 0  1
10	Repeat item 9	Patient compensates. Possible compensations are: (1) use of upper extremities, (2) pushing off with the ipsilateral foot (heel loses contact with the floor) Patient moves without compensation Total dynamic sitting balance	 0  1 /10

Co-ordination

1	Starting position Patient is instructed to rotate upper trunk 6 times (every shoulder should be moved forward 3 times), first side that moves must be hemiplegic side, head should be fixated in starting position	Hemiplegic side is not moved three times Rotation is asymmetrical Rotation is symmetrical If score = 0, then item 2 scores 0	 0  1  2
2	Repeat item 1 within 6 seconds	Rotation is asymmetrical Rotation is symmetrical	 0  1
3	Starting position Patient is instructed to rotate lower trunk 6 times (every knee should be moved forward 3 times), first side that moves must be hemiplegic side, upper trunk should be fixated in starting position	Hemiplegic side is not moved three times Rotation is asymmetrical Rotation is symmetrical If score = 0, then item 4 scores 0	 0  1  2
4	Repeat item 3 within 6 seconds	Rotation is asymmetrical Rotation is symmetrical Total co-ordination	 0  1 /6
Total Trunk Impairment Scale			/23

1-3 PASS

Maintaining a Posture

Give the subject instructions for each item as written below. When scoring the item, record the lowest response category that applies for each item.

1. Sitting Without Support

Examiner: Have the subject sit on a bench/mat without back support and with feet flat on the floor.

- (3) Can sit for 5 minutes without support
- (2) Can sit for more than 10 seconds without support
- (1) Can sit with slight support (for example, by 1 hand)
- (0) Cannot sit

2. Standing With Support

Examiner: Have the subject stand, providing support as needed. Evaluate only the ability to stand with or without support. Do not consider the quality of the stance.

- (3) Can stand with support of only 1 hand
- (2) Can stand with moderate support of 1 person
- (1) Can stand with strong support of 2 people
- (0) Cannot stand, even with support

3. Standing Without Support

Examiner: Have the subject stand without support. Evaluate only the ability to stand with or without support. Do not consider the quality of the stance.

- (3) Can stand without support for more than 1 minute and simultaneously perform arm movements at about shoulder level
- (2) Can stand without support for 1 minute or stands slightly asymmetrically
- (1) Can stand without support for 10 seconds or leans heavily on 1 leg
- (0) Cannot stand without support

4. Standing on Nonparetic Leg

Examiner: Have the subject stand on the nonparetic leg. Evaluate only the ability to bear weight entirely on the nonparetic leg. Do not consider how the subject accomplishes the task.

- (3) Can stand on nonparetic leg for more than 10 seconds
- (2) Can stand on nonparetic leg for more than 5 seconds
- (1) Can stand on nonparetic leg for a few seconds
- (0) Cannot stand on nonparetic leg

5. Standing on Paretic Leg

Examiner: Have the subject stand on the paretic leg. Evaluate only the ability to bear weight entirely on the paretic leg. Do not consider how the subject accomplishes the task.

- (3) Can stand on paretic leg for more than 10 seconds
- (2) Can stand on paretic leg for more than 5 seconds
- (1) Can stand on paretic leg for a few seconds
- (0) Cannot stand on paretic leg

Maintaining Posture SUBTOTAL _____

2. Intervention

2.1 ADIM exercise

The objective of this study is to enhance the strength of the deep core muscles, specifically the Transverse abdominis (TrA) muscle by using a simple device that observes pressure changes with a gauge. ADIM exercise is a functional and requiring precise motor control to engage the relevant muscle with the appropriate level of intensity for targeted muscle control. Pull the navel deeply to the lumbar region using the Stabilizer™ pressure Biofeedback, which stabilizes the TrA muscle (S.-D. Park & Yu, 2013). Participants receive ADIM exercise twice a week for four weeks. Participants were asked to Move from supine to hook-lying (hip joint_ 40°; knee joint_ 80°) (S.-D. Park & Yu, 2013; Yu & Park, 2013). They focus on controlled contractions, gentle breathing, and avoid pelvic and chest movement during the exercise. Each exercise session lasts for 40 minutes, with an additional 10 minutes dedicated to trunk stretching and mobilization exercises for the upper extremities (Ko et al., 2016). Over a 4-week period, participants engaged in an exercise regimen that gradually increased the contraction of the TrA muscle to 40 mmHg, with a limited maximum increased of an additional 2 mmHg (D.-J. Park & Lee, 2013). The exercise involved 10 repetitions per set, with each contraction lasting 5 seconds. This routine was repeated for a total of 10 sets.

2.2 Transcutaneous Electrical Nerve Stimulation (TENS)

The intervention encompassed a range of pain relief techniques, including limb stretching, mobilization of the upper extremity, and targeted pelvic movements. To manage pain, a TENS (EMGFES 1000, Cyber medic, South Korea) was applied to the affected area for a duration of 20 minutes. Additionally, participants engaged in a series of movements while in a supine position, involving trunk rotations to each lateral side, each held for 5 seconds, as well as anterior and posterior pelvic movements with knees flexed at 90 degrees. This regimen comprised 10 repetitions per set, totaling 5 sets. Participants attended two sessions per week over a 4-week period, with each session lasting 40 minutes under the guidance of the same experienced physical therapist. For control of pain, the instrument was applied to pain area with TENS in 20 minutes to upper extremity pain area. And in supine position, trunk movement rotation each lateral side with holding on 5 seconds and pelvic anterior and posterior with knee 90 flexion. The intensity consisted of 10 repetitions per set in total 5 sets. They had two 40-minute sessions per week for 4 weeks. This therapy is guided by a physical therapist with over 10 years of experience.

Safety evaluation criteria and evaluation methods

Before starting the experiments, the health and physical condition of the subjects are assessed, and within 24 hours after the experiment, and signs of physical abnormalities are monitored.

Data analysis and statistical methods

To determine the sample size, the G * Power V.3.1 was utilized (Franz Paul, Kiel, Germany) (Faul F et al., 2007) incorporating an effect size of 0.44, $\alpha < 0.05$, power = 0.80, requiring total sample size of 12 participants (Dos Santos et al., 2019).

1. Statistical analysis was performed with IBM SPSS (version 28.0.1.1 (14)). Data were tested for normality using the Kolmogorov-Smirnov test. Kinematic data did not significantly deviate from a normal distribution ($P > 0.05$). The Chi-square test was used to assess the sex distribution of the participants. The independent *t*-test and Mann-Whitney *U* test, as a nonparametric test, were employed to compare the two groups concerning specific demographic and clinical characteristics.

In the event of an unforeseen emergency, the participant's condition will be assessed, and immediate contact

Predicted side effects and precautions with corresponding measures

will be made with emergency medical personnel for necessary actions. Subsequently, a prompt report will be submitted to the Institutional Review Board (IRB)

Criteria for discontinuation and dropout

1. Inability to independently perform the action of sitting and extending the paralyzed arm
2. Feeling of dizziness

Risks and benefits to research participants

- Prior to the start of the experiment, participants will receive a comprehensive explanation of the entire experimental procedure and the potential risks involved through an informed consent document. They will proceed with the experiment after understanding and acknowledging these risks.
- In the event of an emergency during the experiment, participants will be provided with non-monetary measures to seek medical examination and treatment from a qualified healthcare institution, even after the conclusion of the experiment.

References

Butcher, S. J., Craven, B. R., Chilibeck, P. D., Spink, K. S., Grona, S. L., & Sprigings, E. J. (2007). The effect of trunk stability training on vertical takeoff velocity. *Journal of Orthopaedic and Sports Physical Therapy*, 37(5), 223–231. <https://doi.org/10.2519/JOSPT.2007.2331>

Che-Nan, H., & Rambely, A. S. (2022). Kinematic Analysis of Daily Activity of Touching Lateral Shoulder for Normal Subjects. *Applied Sciences (Switzerland)*, 12(4). <https://doi.org/10.3390/APP12042069>

Dean (1997) 'Task-related training improves performance of seated reaching tasks after stroke. A randomized controlled trial.', *Stroke*, 28(4), pp. 722–8. doi:info:doi/.

Murphy, M. A., Sunnerhagen, K. S., Johnels, B., & Willén, C. (2006). Three-dimensional kinematic motion analysis of a daily activity drinking from a glass: a pilot study. *Journal of Neuroengineering and Rehabilitation*, 3. <https://doi.org/10.1186/1743-0003-3-18>

Murphy, M. A., Willén, C., & Sunnerhagen, K. S. (2011). Kinematic variables quantifying upper-extremity performance after stroke during reaching and drinking from a glass. *Neurorehabilitation and Neural Repair*, 25(1), 71–80. <https://doi.org/10.1177/1545968310370748>

The Effects of Reaching Task Following Selective Trunk Stability Exercise

- **NCT Number: NCT05767437**
- **Protocol Version:1.0**
- **Document Date: July 20, 2022**
- **Study Design: A crossover study comparing ADIM exercise and Conventional therapy**
- **Study Groups:**
 1. Group A (ADIM-CT): ADIM exercise followed by Conventional therapy
 2. Group B (CT-ADIM): Conventional therapy followed by ADIM exercise
- **Sample Size Calculation**
 - Using G*Power Version 3.1 (Franz Paul, Kiel, Germany)
 - Input parameters:
 - Effect size: 0.44
 - Significance level (α): < 0.05
 - Power: 0.80
 - Required total sample size: 12 participants

Although we initially planned to recruit 12 participants in total, considering a potential dropout rate of 10%, we recruited 10 participants per group (20 participants total)

● Statistical Analysis

1. Statistical Software
 - Data analysis was performed using IBM SPSS 14 (version 28.0.1.1)
2. Tests for Normality
 - The Kolmogorov-Smirnov test was used to assess data normality
 - Kinematic data showed normal distribution ($P > 0.05$)
3. Basic Statistical Analysis
 - Sex distribution: Chi-square test
 - Comparison of demographic and clinical characteristics:

- For normally distributed data: Independent t-test
- For non-normally distributed data: Mann-Whitney U test (non-parametric)

4. Crossover Analysis

- Carryover Effect: Analysis combining data from both periods for each group
- Period Effect: Analysis of differences between groups for each treatment
- Treatment Effect: Mixed Analysis of Variance (Mixed ANOVA)
 - Factors: 2 groups \times 3 assessment points
 - Interaction analysis: Analysis of change patterns between groups over time

5. Multiple Comparison Adjustment

- Bonferroni correction method
- Statistical significance level: $P < 0.05$

6. Post-hoc Analysis

- Bonferroni sample t-test
- Pairwise comparisons within each group across three assessment points

7. Clinical Outcome Analysis

- Two-sided unpaired t-test
- Significance level: $P < 0.05$

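### For outcomes analysed by the mixed ANOVA, the SAP's treatment test is a 2-df sequence-by-time interaction that gives no ADIM-minus-comparator estimate or CI, and its only follow-up mixes treatment with period

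*SAP*

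**What the plan says.** The protocol (Methodology and Design) describes a two-period crossover whose purpose is to compare ADIM with TENS; the SAP calls the comparator conventional therapy. Under Study Groups, the SAP defines the groups by order of treatment, for example "Group A (ADIM-CT): ADIM exercise followed by Conventional therapy", and Group B has the reverse order. Every participant therefore receives both treatments, and group means sequence.

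SAP section 4 has three lines:
- Treatment: "Treatment Effect: Mixed Analysis of Variance (Mixed ANOVA", with 2 groups by 3 assessment points and "Interaction analysis: Analysis of change patterns between groups over time".
- Period: "Period Effect: Analysis of differences between groups for each treatment", with no test named.
- Carryover: "Carryover Effect: Analysis combining data from both periods for each group", with no test named.

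Section 6, the post-hoc analysis, specifies "Pairwise comparisons within each group across three assessment points" with a Bonferroni adjustment. Section 7, for clinical outcomes, specifies a "Two-sided unpaired t-test" and does not say what is compared. The three assessment points are not defined. The protocol's statistical section names tests only for normality, sex distribution, and demographic and clinical characteristics. Neither document mentions a confidence interval.

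**The concern.** The trial asks how ADIM compares with the comparator. A significant sequence-by-time interaction says that the two sequences changed differently over three time points. It does not say which treatment did better or by how much. The plan then turns to tests inside each sequence, where the two treatments are always given in different periods. Any learning, practice or time effect between periods is added to the treatment difference in one sequence and subtracted in the other. The report could show a clear result in one group and nothing in the other, with no planned quantity that brings the two together.

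**Working it through.** **The planned test and the plan's own figure.** Interaction df = (2-1)(3-1) = 2. The stated N of 12 is consistent with this test. Take effect size 0.44, alpha 0.05 and power 0.80 from the SAP, and assume Cohen's f, a correlation rho of 0.5 between assessments, and sphericity. Then lambda = f² x N x 3/(1-rho).
- N = 12: lambda = 0.1936 x 12 x 3/0.5 = 13.94 on (2, 20) df, power 0.88.
- N = 10: power 0.797, just short of 0.80.

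The smallest even N is 12, as stated.

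**What each specified analysis estimates.** Assume the points are baseline, end of period 1 (post1) and end of period 2 (post2), with no carryover. Let p1 and p2 be the period means, a and c the effects of ADIM and comparator, and t = a - c.

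| | post1 | post2 | ADIM minus comparator within the sequence |
|---|---|---|---|
| Group A | p1 + a | p2 + c | t - (p2 - p1) |
| Group B | p1 + c | p2 + a | t + (p2 - p1) |

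- Section 6, post1 against post2: neither row equals t unless p2 = p1. Their average is t, so the cell means hold the answer, but section 6 does not combine them.
- Section 6, baseline against post1: both groups are shifted by the same period-1 gain, and each shows one treatment only.
- Period line, read as the same treatment compared between groups: (p1 + a) - (p2 + a) = p1 - p2. Treatment cancels.
- Carryover line, read as a sum over periods: p1 + p2 + a + c in both groups. The treatment difference cancels.

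**Size.** The SAP states "we recruited 10 participants per group (20 participants total", so take 10 per sequence. Assume SD 1, equal correlations, a Bonferroni family of three (0.05/3) and 100,000 simulated trials per setting.
- No treatment difference, common gains: the interaction rejects in 4.9-5.1%.
- t = 0.8, p2 - p1 = 0.5: 0.8 - 0.5 = +0.30 in Group A and 0.8 + 0.5 = +1.30 in Group B. After a significant interaction with rho 0.7-0.8, only Group B is significant in about 87-90%.
- t = 0.8, p2 = p1: +0.80 in both groups, with no distortion.

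**A contrast that combines the sequences.** Take half the between-sequence difference in (period 1 minus period 2), by two-sample t-test on 18 df.

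*Post-period value.*
- No carryover (A: post1 1.3, post2 1.0; B: 0.5, 1.8): 0.5 x [0.3 - (-1.3)] = 0.80, which is t.
- Gains persist, phase gains 0.9 for ADIM and 0.1 for comparator (A: 0.9, 1.0; B: 0.1, 1.0): 0.5 x [-0.1 - (-0.9)] = 0.40, half of the 0.80 difference in phase gains.
- 95% CI half-width = 2.101 x 0.5 x sqrt(2V/10) with V = 2(1-rho): 0.47, 0.36 and 0.30 SD at rho 0.5, 0.7 and 0.8.

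*Change over each period, baseline 0.*
- Gains persist: 0.5 x [(0.9 - 0.1) - (0.1 - 0.9)] = 0.80.
- No carryover: 0.5 x [(1.3 + 0.3) - (0.5 - 1.3)] = 1.20, an overstatement of 0.80.
- Half-width with V = 6(1-rho): 0.81, 0.63 and 0.51 SD at the same rho.

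**Power.**
- Effect present only while on treatment (0.6 SD, rho 0.5): interaction 0.63, post-period contrast 0.72.
- Gains persist (0.8 SD, rho 0.7): interaction 0.62, post-period contrast 0.59, change contrast 0.71.

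**The case against.** The strongest reply is that the planned test is sound. The interaction compares sequences, so a period effect common to both cancels; its size is about 5%; and N = 12 appears to have been set for it. This stands. A reader might infer that the mixed ANOVA is invalid or biased by period, and the documents do not support that. The mixing with period arises in section 6.

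A reader might also infer that nothing in the SAP can deliver the crossover comparison. Section 7 prevents so flat a statement: an unpaired t-test on within-participant period differences would be exactly that comparison. The SAP does not say that this is meant, but it does not exclude it either. For clinical outcomes the fault is ambiguity only.

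A third inference is that within-sequence tests would point the wrong way if gains persist. This does not hold up. In that setting Group A's post1-to-post2 change is just the comparator-phase gain of 0.1 SD. Read as ADIM minus comparator, it is significantly wrong in only 0.9-1.5% of trials with a significant interaction (rho 0.7-0.8), while the ADIM-phase gain is significant in both groups in 74-90%.

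Finally, the post-period contrast is not always the right summary. If gains persist it returns half the effect, with slightly less power than the interaction. This also stands, and it shapes the fix.

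**Conclusion.** The concern holds for the outcomes analysed by the mixed ANOVA, presumably the kinematic ones, since section 7 covers clinical outcomes separately. For these the plan has a valid but non-directional test, no specified ADIM-minus-comparator estimate or interval, and a follow-up whose post1-post2 comparison departs from t by the full period difference, in opposite directions in the two sequences.

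That omission is plain from the text. The size is not: assessment timing, period difference, correlation, persistence of effects and the Bonferroni family are all assumed. A 0.5 SD period difference turns 0.80 into +0.30 and +1.30; a zero difference leaves it intact. The documents give no basis for preferring either. This should be fixed, but it does not invalidate the planned test.

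**What to change.** 1. Define the three assessment points, and state what is assumed about carryover from period 1 into period 2.
2. For each outcome, add the 1-df contrast that combines both sequences, by two-sample t-test, and report ADIM minus comparator with a 95% CI.
3. Choose its form from step 1. Use the post-period value if effects are not expected to persist into period 2. Use change over each period if gains are expected to persist. The change form should be run only as a two-sample t-test, because the two changes share post1 and are negatively correlated (-0.5 under equal correlations).
4. Keep the interaction, on which N = 12 appears to rest, and label the within-sequence tests descriptive.
5. State which samples the section 7 t-test compares.
6. The SAP describes recruitment in the past tense and reports a normality result for the kinematic data. If outcome data had already been seen, label the contrast as added afterwards.

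The cost is SAP wording and one t-test per outcome in the existing software, with no new data or participants. The downsides are that the estimate depends on the carryover assumption (0.8 SD carried into Group A's second period, with no true effect, shifts the post-period contrast by 0.5 x (-0.8) = -0.40 SD), that there is no general power gain over the interaction, and that the contrast may not count as prespecified.

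### Holm's step-down method would be a cheap improvement on the valid single-step Bonferroni correction for the post-hoc within-group comparisons, once the family of tests is stated

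*SAP*

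**What the plan says.** SAP section 5 gives the multiplicity method as the "Bonferroni correction method" with significance at P below 0.05. SAP section 6 names a "Bonferroni sample t-test" and describes its use: "Pairwise comparisons within each group across three assessment points". Three assessment points make three pairs per group, so there are six per outcome over both groups. Neither section says whether the divisor is three or six. Neither says outright that the t-test is paired, and no step-down method is named.

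These comparisons do not carry the treatment effect. SAP section 4 tests that with a mixed ANOVA of two groups by three assessment points, including the interaction. SAP section 7 analyses clinical outcomes with a "Two-sided unpaired t-test", and the SAP does not say whether section 5 reaches those tests. The protocol's data analysis section mentions no multiplicity adjustment.

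**The concern.** Single-step Bonferroni holds every comparison to the strictest threshold, even after others in the family have been rejected. Holm relaxes the threshold after each rejection and needs no further assumption. With 10 participants per group, some real within-group changes could go undeclared only because of the version of the correction chosen. The loss falls on the second and third comparisons, so it matters when the reader wants to know between which assessments change occurred, and not merely whether any change occurred.

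**Working it through.** **Inputs from the documents.** Three assessment points, alpha 0.05 and 10 participants per group (SAP). The sample-size statement is "Required total sample size: 12 participants", "incorporating an effect size of 0.44" and power 0.80.

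**Assumptions, because the documents are silent.** Paired two-sided t-tests, a family of three tests per group, and the correlations and shifts shown in the table.

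**1. The plan's own figure.** The SAP does not name the G*Power test. Take 0.44 as Cohen's f in a repeated-measures interaction test with g = 2 groups, m = 3 measurements and an assumed correlation of 0.5:

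- lambda = f² × N × m / (1 − rho) = 0.1936 × 12 × 3 / 0.5 = 13.94
- df = (g − 1)(m − 1) = 2 and (N − g)(m − 1) = 20
- power = 0.882, and 12 is the smallest even N that reaches 0.80

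The figure depends on the correlation: 0 gives N = 20, 0.3 gives 14 and 0.7 gives 8. Read instead as a standardised mean difference, 0.44 would need 43 for a paired two-sided t-test. The stated 12 is therefore consistent with the ANOVA and not with the pairwise tests, and the choice of correction does not affect it.

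**2. Thresholds.**

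- k = 3: Bonferroni uses 0.05/3 = 0.0167 for every test. Holm uses 0.05/3 = 0.0167, 0.05/2 = 0.025 and 0.05/1 = 0.05 in order of P-value.
- k = 6: Bonferroni uses 0.05/6 = 0.0083 for every test. Holm starts there and relaxes.

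The smallest P-value meets the same threshold under both, so the chance of at least one rejection is identical.

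**3. Power.** Simulation of 40,000 groups of 10, k = 3. Shifts are in SD from the first assessment to the second and third. Pairs are in the order 1–2, 1–3, 2–3. A dash marks a pair with no true difference. The 0.8/0.8/0.6 pattern means 0.8 for adjacent assessments and 0.6 for first to last.

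| Correlations | Shifts | Bonferroni, % | Holm, % | Gain, points |
|---|---|---|---|---|
| all 0.5 | 0.44, 0.44 | 11 / 11 / – | 12 / 12 / – | 1 / 1 |
| all 0.5 | 0.7, 0.7 | 30 / 30 / – | 33 / 33 / – | 3 / 3 |
| all 0.5 | 0.6, 0.9 | 22 / 50 / 6 | 26 / 52 / 8 | 4 / 2 / 2 |
| all 0.5 | 0.7, 1.2 | 30 / 78 / 15 | 38 / 80 / 22 | 8 / 2 / 7 |
| 0.8/0.8/0.6 | 0.6, 0.9 | 55 / 61 / 13 | 62 / 65 / 23 | 7 / 4 / 10 |
| 0.8/0.8/0.6 | 0.7, 1.2 | 70 / 87 / 39 | 81 / 89 / 57 | 11 / 2 / 18 |

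Repeat runs differ by about one point. The chance of declaring all three pairs in the last row is 27% with Bonferroni and 52% with Holm. With the same shifts and correlations of 0.5 it is 2% and 9%.

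The rows differ because the standardised difference depends on the correlation: SD of a difference = √(2(1 − rho)). For pair 2–3 with shifts 0.7 and 1.2, the difference is 0.5 SD. Divided by √(2 × 0.5) = 1 it stays 0.5. Divided by √(2 × 0.2) = 0.632 it becomes 0.79.

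**4. Error control.** With no true effect, family-wise error is equal under the two methods: 4.6% for both at correlation 0.5, and 4.2% for both at 0.8/0.8/0.6. With two true differences and one null, Holm uses more of the allowance but stays within 5%: 3.0% against 1.7% for shifts of 0.88, and 4.1% against 1.7% for shifts of 1.2. Holm lost no Bonferroni rejection in any run.

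**The case against.** The strongest reply is that Bonferroni is valid, so nothing in the SAP is wrong. That stands: this is a suggestion and does not correct a mistake.

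Bonferroni also has simultaneous confidence intervals that match its tests, and Holm has no equally simple ones. If intervals stay at the Bonferroni level, a pair can be declared different while its interval includes zero. In the last row of the table that would happen for pair 2–3 in 57 − 39 = 18% of groups. This stands as a real downside, so a reader who took the gain to be free would go too far. It is a small one here, because the SAP promises no intervals for these contrasts.

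Timing is a further objection. The SAP is partly in the past tense and already reports that the kinematic data were normally distributed. A move to a more liberal rule after results are known invites criticism. The documents do not show whether the post-hoc results had been seen, so the fix has to cover both cases.

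Finally, the large gains need high correlations and steadily increasing means, which the documents do not supply. This also stands, and it is why the result is given as a range.

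**Conclusion.** The point holds as a cheap improvement of low importance. Holm is uniformly at least as powerful as the planned correction, within the same family-wise bound and under any dependence. With 10 per group and k = 3, the gain runs from roughly 2 to 8 points for most real contrasts at correlations of 0.5 (nearer 1 in a few cases) to about 18 points for one pair in the most favourable pattern tried. All these figures rest on assumed correlations, shifts and paired tests.

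Three stronger readings are tempting, and the documents support none of them:

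- **That the treatment conclusion or the sample size suffers.** Treatment is tested by the mixed ANOVA, and the 12 does not come from the pairwise tests.
- **That the plan fixes a threshold of 0.0167.** No divisor is given, and six tests would make it 0.0083. This undefined family is the more material gap of the two.
- **That the post-hoc comparisons are known to be short of power.** No expected within-group shift is stated, and Bonferroni power in the table runs from 6% to 87% according to what is assumed.

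**What to change.** In SAP sections 5 and 6:

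- Replace Bonferroni with Holm. Order the k unadjusted P-values, compare the smallest with 0.05/k, the next with 0.05/(k − 1), and so on, stopping at the first that is not significant.
- State the family: for example k = 3 pairs within each group, per outcome, or k = 6 if both groups form one family. State also that the t-tests are paired and two-sided, if that is the intention, and whether section 5 applies to any other tests.
- Add one sentence saying that any confidence intervals are at the Bonferroni level and may include zero where Holm rejects.
- If post-hoc results have already been seen, label the change as post hoc and report both Bonferroni- and Holm-adjusted P-values.

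The cost is a few lines of SAP wording and a sort of three or six unadjusted P-values per outcome, by hand or in SPSS syntax. No new data are needed. If the sponsor prefers to keep Bonferroni so that tests and intervals agree, that is defensible, but the family still needs to be stated.
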